2.7.4 Assess the time-to-escape during treatment of osilodrostat

Escape is defined as the first loss of control of UFC that meets all of the following criteria:

- prior normalization of UFC has occurred ($mUFC \leq ULN$)
- patient reached highest tolerated dose of osilodrostat
- 2 consecutive $mUFC$ (collected at scheduled visits) were above 1.3x ULN
- the loss of control of UFC is not related to a dose interruption or dose reduction due to safety reasons

- happens beyond Week 26 when the patients have a chance to be treated with doses as high as 30 mg bid

Time-to-escape is defined as the time (in weeks) from the first collection of post-baseline normal mUFC (\leq ULN) to the first mUFC $> 1.3 \times$ ULN on 2 consecutive scheduled visits on the highest tolerated dose of osilodrostat and not related to a dose interruption or dose reduction due to safety reasons after Week 26.

The highest tolerated dose is defined as

- 30 mg bid if reached, or
- being on a reduced dose due to safety reasons such as AEs, or
- being on the same dose for at least 3 scheduled visits if the previous two criteria are not met.

For patients who attained normal mUFC (\leq ULN), time-to-escape will be analyzed using Kaplan-Meier plots. This will be performed by randomized treatment assignment and for the overall trial population using FAS. The quartiles of time to escape and corresponding two-sided 95% confidence interval will be calculated using Kaplan-Meier methodology. In addition, time-to-escape will be summarized using descriptive statistics for patients who escape. Time-to-escape will not be assessed for patients during the first 26 weeks.

Patients that have dose interruption or dose reduction for safety reasons will be censored at the time of the first dose interruption. Patients who discontinued the study are considered as censored. Patients who were controlled until the end of the study will be censored at the last mUFC collection date. FAS will be used for this analysis.

The results of time-to-escape during treatment of osilodrostat up to Week 48 (secondary objective) were reported in the interim CSR, and will not be repeated for the final CSR. Time-to-escape up to end of study will be presented.

2.7.5 Assess the change from baseline in cardiovascular and metabolic related parameters associated with Cushing's disease during the core period of the study

For cardiovascular and metabolic parameters associated with Cushing's disease (e.g. fasting glucose, HbA1c, fasting lipid profile, SBP, DBP, weight and waist circumference):

For actual value and change from baseline to Week 12, Week 36 and Week 48, descriptive summaries were reported in the core CSR. Additional information from further visits including the extension period will be provided.

FAS will be used for this analysis.

2.7.6 Assess the change from baseline in physical features of Cushing's disease

For each of physical features of Cushing's disease: facial rubor, striae, supraclavicular fat pad, dorsal fat pad, proximal muscle wasting (atrophy), central (abdominal) obesity, and ecchymoses (bruises), Likert scores will be measured. The change from baseline at scheduled visits will be

summarized. This includes the proportions of patients having a favorable shift from baseline to post-baseline time points. FAS will be used for this analysis.

2.7.7 Assess the change from baseline in bone mineral density by DXA scan

For bone mineral density measured by DXA scan at the lumbar spine and total hip, descriptive summaries of actual and percentage change from baseline to Week 48, Week 96 and EOT Extension will be provided by randomized treatment arm and for overall patients. FAS will be used for this analysis.

2.7.8 Assess the change from baseline in serum, salivary and hair cortisol levels

The actual and percentage change from baseline to each post-baseline visit for serum cortisol, late night salivary cortisol, morning salivary cortisol and hair cortisol levels will be assessed. Descriptive summaries will be provided for every visit in the Core and Extension phases at which the cortisol markers are collected. Salivary cortisol samples will only be included if they are collected within the correct time window. 95% CIs for the percentage change from baseline will also be provided by treatment arms and for all patients.

2.8 Safety analyses

The assessment of safety will be based mainly on the frequency and severity of AEs and on the number of laboratory values that fall outside of pre-determined ranges. Other safety data (e.g. ECG, findings from Holter recordings, vital signs, and special tests) will also be presented.

In the Final CSR results for the overall study period will be analyzed using the SS. Safety analyses presented for the placebo-control period in the interim CSR will not be repeated. Safety analyses for overall study period will focus solely on the safety of osilodrostat treatment. The analyses include the osilodrostat arm besides the placebo arm excluding placebo-control period, and overall patients (excluding safety data of placebo arm collected during placebo-control period).

The overall observation period will be divided into three mutually exclusive segments:

- pre-treatment period: from day of patient's informed consent to the day before first dose of study medication
- on-treatment period: from day of first dose of study medication to 30 days after last dose of study medication
- post-treatment period: starting at 31 days after last dose of study medication.

2.8.1 Adverse events (AEs)

Summary tables for adverse events (AEs) have to include only AEs that started or worsened during the on-treatment period, the *treatment-emergent* AEs. However, all safety data (including those from the pre and post-treatment periods) will be listed and those collected during the pre-treatment and post-treatment period are to be flagged.

The incidence of treatment-emergent adverse events (new or worsening from baseline) will be summarized by system organ class and or preferred term, severity (based on CTCAE version 4.03 grades), type of adverse event, relation to study treatment.

Serious adverse events, non-serious adverse events and adverse events of special interest (AESI) during the on-treatment period will be tabulated.

All AEs, deaths and serious adverse events (including those from the pre and post-treatment periods) will be listed and those collected during the pre-treatment and post-treatment period will be flagged. A separate listing including any suspected or confirmed SARS-Cov-2 infections will be provided.

AEs will be summarized by number and percentage of subjects having at least one AE, having at least one AE in each primary system organ class (SOC) and for each preferred term (PT) using MedDRA coding. A subject with multiple occurrences of an AE will be counted only once in the respective AE category. A subject with multiple CTCAE grades for the same preferred term will be summarized under the maximum CTCAE grade recorded for the event.

In AE summaries the primary system organ class will be presented alphabetically and the preferred terms will be sorted within primary SOC in descending frequency. The sort order for the preferred term will be based on their frequency in the osilodrostat arm.

The following adverse event summaries will be produced by treatment; overview of adverse events and deaths (number and % of subjects who died, with any AE, any SAE, any drug reductions/interruptions), AEs by SOC and PT, summarized by relationship (all AEs and AEs related to study treatment), seriousness (SAEs and non-SAEs), leading to treatment discontinuation, leading to dose interruption/adjustment, requiring additional therapy and leading to fatal outcome. In addition, for the summary of serious and non-serious adverse events the number of occurrences will be produced (an occurrence is defined as >1 day between start and prior end date of record of same preferred term).

Additional exploratory analyses may be done to assess the impact of COVID-19 pandemic on adverse event reporting.

2.8.1.1 Adverse events of special interest / grouping of AEs

Groupings of AEs of special interest consist of adverse events for which there is a specific clinical interest in connection with LCI699 treatment (i.e. where LCI699 may influence common mechanism of action responsible for triggering them) or adverse events which are similar in nature (although not identical). The list of AESIs is updated periodically after MedDRA update and/or review of accumulating trial data and defined in the eCRS (electronic Case Retrieval Strategy) in the DMS (Document Management System). The most up-to-date version of the CRS will be used at the time of analysis.

For each specified AESI, number (%) of participants with at least one event of the AESI occurring during on treatment period will be summarized together with the individual preferred terms in that grouping. In addition, number (%) of participants with at least one AESIs by maximum CTC grade, related AESIs, serious AESIs as well as action taken and outcome of the respective AESI will be summarized.

All adverse events of special interest will be listed.

2.8.1.2 Adverse events by time of onset

AEs will also be categorized by the time of onset, and separate summaries shown for defined time periods of the study.

The time periods used will be

- Baseline to Week 12
- Week 12 to Week 24
- Week 24 to Week 36
- Week 36 to Week 48
- Week 48 to Week 60
- Week 60 onwards

The denominator for each time period will be the number of patients still on the study at the start of that period. These summaries will be reported for

- Adverse events of Special Interest, regardless of study drug relationship, by category and preferred term
- Adverse events of Special Interest with suspected study drug relationship, by category and preferred term

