2.8 Safety analyses

The assessment of safety will be based mainly on the frequency and severity of AEs and on the number of laboratory values that fall outside of pre-determined ranges. Other safety data (e.g. ECG, vital signs, and special tests) will also be presented. All safety outputs will use the SS, which consists of all patients who received at least one dose of osilodrostat or placebo. Safety data will be presented by two different periods in different treatment groups as described below.

- Placebo-control period: osilodrostat arm, placebo arm

- Overall study period: osilodrostat arm, placebo arm excluding placebo-control period, and overall patients (excluding safety data of placebo arm collected during placebo-control period)
 - * Safety summarized during overall study period focuses on safety of osilodrostat treatment, safety of placebo arm is summarized during placebo-control period.

The overall observation period will be divided into three mutually exclusive segments:

- pre-treatment period: from day of patient's informed consent to the day before first dose of study medication
- on-treatment period: from day of first dose of study medication to 30 days after last dose of study medication
- post-treatment period: starting at 31 days after last dose of study medication.

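### The open-ended last onset window for adverse events of special interest gives a crude percentage that cannot be compared with the five 12-week windows before it

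*SAP*

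**What the plan says.** **Onset table.** Final SAP (1 December 2020), section 2.8.1.2, uses five windows of 12 weeks from baseline, the fifth being "Week 48 to Week 60", and then "Week 60 onwards", which has no upper end. On the denominator it states: "The denominator for each time period will be the number of patients still on the study at the start of that period". The table covers AESIs only, once as "Adverse events of Special Interest, regardless of study drug relationship, by category and preferred term" and once restricted to events with suspected relationship.

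**Overall-period tables.** Section 2.8.1 of both SAPs gives the measure: "AEs will be summarized by number and percentage of subjects having at least one AE". For AESIs, final SAP 2.8.1.1 reports the "number (%) of participants with at least one event of the AESI occurring during on treatment period". The columns in the core SAP (1 April 2019), section 2.8, are "osilodrostat arm, placebo arm excluding placebo-control period, and overall patients". Final SAP 2.8 keeps that layout: "The analyses include the osilodrostat arm besides the placebo arm excluding placebo-control period, and overall patients".

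**Length of follow-up.** Protocol 6.1.5 ends the extension at Week 96, or within 4 weeks of local approval of Amendment 02 if that comes first. Core SAP 1.1.4 expects some patients to stay past Week 96, final SAP 1.1.4 describes that option as it stood before Amendment 02, and final SAP 2.3.2 has a disposition row for discontinuation after Week 96.

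**Exposure.** Both SAPs summarise duration of exposure in section 2.4.1.1. Neither uses it as the denominator of an AE rate, and neither plans a time-to-first-event analysis for AEs.

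**The concern.** A percentage of patients with at least one event depends on how long they were watched. The five early windows share one nominal length, so their percentages can be read against each other. The sixth can last a few weeks for one patient and well over half a year for another, yet each counts as one in the denominator. A reader scanning across the row would take a jump or a drop in the last column as a change in risk, when it may reflect only the length of observation. The AESI groups in Protocol 8.1.3 include hypocortisolism, QT prolongation and precursor accumulation, and long-term safety is a stated purpose of the final report.

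The overall-period tables carry a milder form of the same problem. The osilodrostat arm is observed on drug from Day 1, the placebo arm only from Week 12, and the two stand side by side as crude percentages.

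**Working it through.** **1. The plan's own exposure figure.** Protocol 6.1.5 gives 36 to 48 weeks on osilodrostat in the Core phase. The 48-week Core less the 12-week placebo period is 36 weeks for the placebo arm, against 48 for the osilodrostat arm. This agrees. If both arms reach Week 96, the exposures are 96 and 84 weeks.

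**2. Length of the last window.** From Week 60 to Week 96 is 36 weeks, three times an earlier window. This counts study weeks from Day 1. Section 2.8.1.2 does not say whether placebo-arm weeks run from randomisation or from first osilodrostat dose. On the second reading the full last window for that arm is 84 − 60 = 24 weeks.

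**3. Formula.** Let r be an assumed constant risk of a first event per 12 weeks. Over w weeks, P = 1 − (1 − r)^(w/12). The documents give no AE rate, so r is varied.

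| r per 12 weeks | Each earlier window | Full Week 60-96 (36 weeks) | Overall period, 96 vs 84 weeks |
|---|---|---|---|
| 5% | 5% | 14.3% | 33.7% vs 30.2% |
| 10% | 10% | 27.1% | 57.0% vs 52.2% |
| 20% | 20% | 48.8% | 83.2% vs 79.0% |
| 30% | 30% | 65.7% | 94.2% vs 91.8% |

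For example, 1 − 0.9³ = 0.271, 1 − 0.9⁸ = 0.570 and 1 − 0.9⁷ = 0.522. For a 24-week last window, 1 − 0.9² = 0.190.

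**4. Realised follow-up after Week 60.** The Protocol's amendment rationales give two anchors. Eighteen patients had been enrolled by 20 November 2017. The last patient was due to finish Week 48 by the end of February 2020, hence entered about the end of March 2019. Further assumptions: 69 patients, linear enrolment between these dates, no dropout, a cap at Week 96, and exit between April and October 2020. The mean time after Week 60 is then about 29 to 34 weeks, and 0 to 13% of patients have under 12 weeks. At r = 10%, the expected last-window figure is about 22 to 26%. The cap leaves out continuation past Week 96, and the no-dropout assumption is generous, so this is only a rough guide.

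**5. The opposite direction.** A patient who leaves 6 weeks into the last window contributes 1 − 0.9^0.5 = 5.1%, below the 10% of an earlier window.

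**6. Front-loaded risk, by arm.** Assume 20% in the first 12 weeks on drug, with the hazard halving every 12 weeks. The cumulative hazard after k blocks is −ln(0.8) × (2 − 2^(1−k)). At 96 weeks (k = 8), P = 1 − 0.8^1.9922 = 35.9%. At 84 weeks (k = 7), P = 1 − 0.8^1.9844 = 35.8%. The crude gap between arms almost disappears.

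**7. A single overall rate under the same front-loaded risk.** First events divided by person-time at risk give 0.28 per patient-year at 96 weeks and 0.31 at 84 weeks. The arm with longer exposure would look about 11% safer, although both arms follow the same risk curve.

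**The case against.** Much can fairly be said for the plan. The five equal windows cover the whole Core phase, both titrations and the first 12 weeks of the extension, and the last column's label shows that it is open-ended. The tables are descriptive, without a between-arm test. The core SAP compares the randomised arms over an equal 12 weeks, and exposure duration is reported separately. Constant risk is also a doubtful model here: Protocol 6.3.2 and 8.1.3.2 tie glucocorticoid withdrawal to a rapid fall in cortisol, and the extension dose is held unless a change is needed.

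These points narrow the concern without removing it. A reader might infer stronger versions that the documents do not support:

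- *That the table cannot show how AESIs change with time on drug.* It can up to Week 60, subject to dropout within a window; only the last column fails.
- *That AESIs must appear to rise after Week 60.* Exits under Amendment 02 shorten the window and pull the figure down.
- *That the last column could approach 47%.* At r = 10%, 46.9% needs 72 weeks after Week 60, so every patient followed to Week 132. Only some were expected to pass Week 96.
- *That the arms would differ as at 48 against 36 weeks (34.4% vs 27.1% at r = 10%).* No planned overall table stops there. Core SAP sections 1 and 2.4.1.1 bring in extension data up to cut-off, and the final SAP runs to study end.
- *That one overall exposure-adjusted rate would settle the by-arm comparison.* Step 7 shows that it can mislead when risk falls with time.

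**Conclusion.** The concern holds for the last onset window. Its crude percentage is not comparable with the earlier five because its length differs from them and between patients. At an assumed constant 10% per 12 weeks it would show 27.1% if every patient were followed from Week 60 to Week 96, and about 22-26% under the rough follow-up estimate, against 10% in each earlier window. The direction in the actual data is not fixed, and a reader of the planned table could not tell which effect prevailed.

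The by-arm point is secondary. Twelve more weeks on drug gives 57.0% against 52.2% at 96 and 84 weeks under the same assumption, and almost no gap if risk is concentrated early. All these sizes rest on assumed event rates; the unequal lengths come from the documents. The effect is on how long-term and by-arm safety figures are read. The primary and key secondary analyses and the randomised 12-week safety comparison are untouched.

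**What to change.** In final SAP 2.8.1.2, replace the open-ended window with Weeks 60-72, 72-84, 84-96 and beyond 96. Section 2.3.2 already uses Weeks 72 and 96 as cut points for disposition. Pool adjacent late windows that have fewer than 15 patients, the threshold that section 2.1.1 sets for reporting an extension time point. In every window show patients at risk, person-time on osilodrostat and first events per patient-year with a 95% CI, alongside the crude percentage. Under a constant 10% per 12 weeks, each window would then show the same rate: −ln(0.9) ÷ (84/365.25) = 0.46 per patient-year. State how the 30-day on-treatment tail is treated, in the same way for events and for person-time.

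In the overall-period AESI tables, keep the crude percentages and add total osilodrostat person-time by arm, counted from the first osilodrostat dose. This needs a clear definition. The formula in final SAP 2.4.1.1 starts at the first study-treatment date, which section 2.1.1 defines as the first Period 1 dose, while the text of 2.4.1.1 excludes placebo exposure. Read literally, the formula would add about 12 weeks per placebo-arm patient. Any single overall exposure-adjusted rate should be supplementary, with a note that it assumes a roughly constant hazard.

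The cost is a few extra table columns derived from dose and AE dates already collected, and some small late denominators with wide intervals.

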1.1.3 Period 2 (Weeks 12-48, open-label period)

Period 2 started immediately after the Week 12 visit, when the trial became open-label with all patients receiving the active drug, osilodrostat. During Period 2 patients randomized to placebo switched to osilodrostat and underwent their first dose titration with active drug, while patients randomized to osilodrostat continued this treatment and underwent another dose titration.

During Period 2, the investigator was responsible for dose titration. Osilodrostat was titrated up to a maximum dose of 30 mg b.i.d. during this period. Dose titration decisions were made by the investigator based on mean urinary free cortisol (mUFC) results and other relevant patient data.

Three 24-hour urine samples were collected by patients immediately prior to the Week 36 visit (key secondary endpoint) and Week 48 (end of Core phase), two 24-hour samples were collected prior to all other visits in Period 2. A patient was considered to have reached a stable efficacious dose when mUFC remains \leq ULN. This dose was continued, unless a change was needed.

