2.1.1 General definitions

Study drug

Throughout the SAP, investigational drug refers to osilodrostat, and study treatment/ study drug refers to osilodrostat or placebo.

Overall study period

The overall study period refers to the complete study duration (including core and extension period) with data presented by the osilodrostat arm, placebo arm excluding placebo-control period, and overall patients (excluding data of placebo arm collected during placebo-control period).

Date of study treatment

The start date of study treatment is defined as the first date when a nonzero dose of study treatment was administered and recorded on DAR eCRF. The date of first administration of study treatment in period 1 will be referred as the start date of study treatment.

The last date of study treatment is defined as the last date when a nonzero dose of study drug was administered and recorded on DAR eCRF.

Study day

Study day is used to represent an evaluation, a measurement or an event (e.g. AE onset, laboratory abnormality occurrence, disease progression, etc.). The study day is calculated as

Study day = date of assessment – start date of study treatment + 1 (if date of assessment is after start date of study treatment)

Study day = date of assessment – start date of study treatment (if date of assessment is before start date of study treatment)

For any assessment or events such as baseline characteristics or medical history that is supposed to occur prior to start date of the study treatment, study day will be negative. There is no Day 0 defined.

Study day associated with a UFC assessment

The study day associated with a UFC assessment at any particular visit is defined as the study day of the last UFC sample collection for that visit.

Calculating mean UFC

It is scheduled to collect three individual 24 hours Urine Free Cortisol (UFC) samples at visits Week 1, 12, 36, and 48, and two UFC samples at all other visits. For a given visit, Mean Urine Free Cortisol (mUFC) is the mean of all available (with a minimum of 2) individual UFC values determined at a central laboratory. In the case that only one or no UFC value is available, the mUFC will be considered missing for that visit.

Calculation of proportions of responders

All randomized patients will be included in the analysis for calculating the proportion of responders at time points up to Week 48 based on the FAS.

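### Final SAP 2.8.1.2 counts AESI onset in study weeks over all patients on study, so its overall column does not show risk by time on osilodrostat

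*SAP*

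**What the plan says.** All references are to the final SAP (01-Dec-2020) unless stated otherwise.

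- **Windows.** Section 2.8.1.2 states: "AEs will also be categorized by the time of onset, and separate summaries shown for defined time periods of the study". There are six windows, from Baseline to Week 12 through Week 60 onwards. They are used for two AESI summaries, one regardless of relationship to study drug and one limited to suspected relationship.
- **Denominator.** The same section states: "The denominator for each time period will be the number of patients still on the study at the start of that period". It makes no reference to arm or to being on osilodrostat.
- **Time origin.** Section 2.1.1 states: "The date of first administration of study treatment in period 1 will be referred as the start date of study treatment". That first dose may be osilodrostat or placebo.
- **Scope.** Section 2.8 states: "Safety analyses for overall study period will focus solely on the safety of osilodrostat treatment". It drops placebo-arm safety data from the placebo-controlled period.
- **Columns.** Section 2.8.1.2 lists none. Section 2.1.1 defines the overall study period as having "data presented by the osilodrostat arm, placebo arm excluding placebo-control period, and overall patients".
- **Start of drug.** Section 1.1.3 states: "During Period 2 patients randomized to placebo switched to osilodrostat and underwent their first dose titration with active drug". The sentence goes on: "while patients randomized to osilodrostat continued this treatment and underwent another dose titration".

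**The concern.** A reader uses a table of AESIs by time of onset to see when these events occur after starting osilodrostat. Protocol 8.1.3.2 attributes glucocorticoid withdrawal to relatively rapid correction of hypercortisolism, and hypocortisolism to excessive inhibition of cortisol synthesis. Time since starting the drug is therefore the natural scale.

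Study week equals time on osilodrostat only in the arm randomized to it; the placebo arm runs 12 weeks behind. This raises two separate problems in the overall column:

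1. **First window.** The numerator is limited to osilodrostat, but the written denominator is not. The reported percentage then depends on whether the programmer carries the exclusion into the denominator.
2. **Second window.** Patients in their first 12 weeks on drug are pooled with patients in their second 12 weeks.

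The SAP makes the matching adjustment for duration of exposure, where section 2.4.1.1 removes placebo exposure. It does not do so here. Being on study also differs from being on drug: under protocol 7.1.4, a patient who stops study drug is not thereby withdrawn from the study.

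**Working it through.** **Planned numbers.** Section 2.8.1.2 gives no figure of its own. The sizes come from sections 1.1 and 3: 42 + 21 = 63 patients, 63 × 1.10 = 69.3, so about 69. Split 2:1, this is 46 osilodrostat and 23 placebo, as the plan states.

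**Assumed risks.** The documents give no AESI risk by time on drug. Let r1 be the risk in the first 12 weeks on osilodrostat and r2 the risk in the next 12, taken as equal in both arms.
- For r1, protocol 2.3 reports hypocortisolism in 4 of 12 patients over 10 weeks in Part I of the Phase II study, which is 33.3%. This is an illustration only.
- For r2, 5%, 10% and 20% are assumed.
- Dropout within windows is ignored unless stated.

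**Overall column, Baseline to Week 12**
- Literal denominator, placebo-period events excluded: r1 × 46/69 = 33.3% × 0.667 = 22.2%.
- Exclusion applied to the denominator too: r1 × 46/46 = 33.3%, with no dilution.

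The same data can thus yield 22.2% or 33.3%, and section 2.8.1.2 does not say which.

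**Overall column, Week 12 to Week 24**

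If all 23 placebo-arm patients switch, the figure is (46 × r2 + 23 × r1)/69. If only 12 switch, it is (46 × r2 + 12 × r1)/58. Both use r1 = 33.3%.

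| Assumed r2 | All 23 switch | 12 switch |
|---|---|---|
| 5% | 14.4% | 10.9% |
| 10% | 17.8% | 14.8% |
| 20% | 24.4% | 22.8% |
| 33.3% (equal to r1) | 33.3% | 33.3% |

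The mixing does not depend on the first-window denominator, because by then the switched placebo-arm patients are on drug and belong in it. It disappears only when r2 = r1.

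**Both effects together.** With assumed risks of 30% then 15%:
- Literal rule: 0.30 × 46/69 = 20% in the first window and (0.15 × 46 + 0.30 × 23)/69 = 20% in the second.
- First-window denominator limited to the osilodrostat arm: 30%, then still 20% rather than 15%.

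**By-arm columns**
- Osilodrostat arm: on drug from Day 1, so neither effect arises.
- Placebo arm: its first 12 weeks on drug appear, undiluted, under Week 12 to Week 24. Its first window, taken literally, would be zero events over about 23 patients not yet on osilodrostat.

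**Counted from first osilodrostat dose.** With r1 = 33.3%, the first window shows 33.3% (23 expected events in 69 patients) and the second shows r2.

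**The case against.** The strongest reply has five parts.

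- **The exclusion may already cover the denominator.** Sections 2.1.1 and 2.8 exclude placebo-arm data from the placebo-controlled period. Applied to numerator and denominator alike, there is no dilution. This stands as a possible reading, but 2.8.1.2 states its own denominator and does not refer to the exclusion.
- **The time course is visible by arm.** This stands. A reader might infer that the tables hide early risk altogether; the documents do not support that, since only the overall column is affected.
- **First-12-week safety is reported elsewhere.** Section 2.8 of the core SAP (01-Apr-2019) presents the placebo-controlled period by arm, and the final SAP says this will not be repeated. This also stands and limits the consequence.
- **Week 12 to 24 is a titration window for both arms.** Section 1.1.3 and protocol 4.1 have the osilodrostat arm titrated again after Week 12. Events there can be genuine, and r2 may be close to r1. A reader might infer that a halving of risk will be shown as flat; that follows only from the assumed 30% and 15%, which have no source in the documents.
- **Study weeks are a defensible scale.** Under protocol 4.1, Week 12 separates blinded titration by independent endocrinologists (maximum 20 mg b.i.d.) from open-label titration by investigators (maximum 30 mg b.i.d.). A first window counted from first osilodrostat dose would pool the two settings. This is a reason to keep the study-week tables by arm alongside the new version.

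**Conclusion.** The point holds for the overall column.

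- **Baseline to Week 12.** The stated denominator, applied as written, multiplies the on-drug incidence by 46/69 = 0.67 at the planned numbers. This is conditional, because carrying the placebo-period exclusion into the denominator removes it. It would be wrong to say that the plan certainly understates first-12-week risk.
- **Week 12 to Week 24.** Under either denominator the figure mixes first and second 12 weeks on drug, so it is not a risk by time on drug unless the two risks are equal. Its size rests on assumed rates: with r1 = 33.3%, an r2 of 5% to 20% would appear as 14.4% to 24.4% if all 23 placebo-arm patients switch.

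Apart from the placebo arm's first window, the by-arm columns are not distorted. The tables are descriptive, and no hypothesis test, primary result or key secondary result is affected. The change is still worth making, because one permitted reading gives a wrong overall percentage.

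**What to change.** In final SAP 2.8.1.2:

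1. Set the denominator, for each window and column, to patients who have started osilodrostat and who at the start of the window are on it or within 30 days of the last dose. The 30 days match the on-treatment period in section 2.8. Placebo-arm patients who never received osilodrostat then drop out.
2. Leave the placebo-arm column blank before Week 12.
3. Add a version with windows in weeks since the first osilodrostat dose: Day 1 for the osilodrostat arm, the first Period 2 dose for the placebo arm.
4. Keep the study-week tables by arm.

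The cost is SAP wording, one derived date from the dosing record and one extra set of tables. No new data are needed. Fewer placebo-arm patients will reach the latest on-drug windows. The first on-drug window will pool blinded and open-label titration, so the new version should also be shown by arm.
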